2.4.2.4 Previous MS disease modifying treatment

Data collected from the Previous MS disease modifying treatment pages will be summarized separately.

2.5 Analysis of the primary objective

2.5.1 Primary endpoint

The primary variables are pharmacokinetic endpoints, namely AUC_{tau} and C_{max} calculated from PK concentration data collected in the dosing interval after Week 8 dose administration in accordance with the assessment schedule.

All completed subjects in the BE analysis set (as defined in [Section 2.2](#)) will be included in the primary analysis. Concentrations will be given in mass per volume units. Missing values or those below the limit of quantification (LOQ) will be indicated in the data listings and potentially flagged for exclusion in data presentations and calculations. If values are missing

during the dosing interval after Week 8 dose administration having an impact to the validity of the PK assessment, the pharmacokinetic parameters of the affected patient may be excluded from the BE analysis. Furthermore, concentrations will be flagged and indicated in the data listing for exclusion from the BE analysis in case one or more doses were missed up to and including the Week 8 dose administration, which will also lead to exclusion of the pharmacokinetic parameters of the patient from the BE analysis. Pharmacokinetic parameters, expressed either as mean, SD, and CV, with any geometric means indicated, or as median and range of values, will be determined using non-compartmental method(s) with Phoenix WinNonlin (Version 6.2 or higher).

2.5.2 Statistical hypothesis, model, and method of analysis

To address the primary objective of testing bioequivalence between PFS and AI, the primary analysis involves the two groups (PFS (abdomen) and AI (abdomen)). In the following, the PFS (abdomen) group will be referred to as the Reference (or R) group and the AI (abdomen) group as the Test group (or T).

The null hypothesis is that “Mean difference in $\ln(\text{AUC}_{\text{tau}})$ and/or $\ln(\text{C}_{\text{max}})$ greater than allowed-difference between these 2 groups” ($H_0: |\mu_T - \mu_R| > \Delta$). The alternative hypothesis is that “Mean difference in $\ln(\text{AUC}_{\text{tau}})$ and $\ln(\text{C}_{\text{max}})$ less than allowed-difference between these 2 groups” ($H_a: |\mu_T - \mu_R| \leq \Delta$). \ln refers to the natural log function. The testing procedure is described below.

As the testing for Average Bioequivalence (ABE) will be based on a between-groups comparison, the variabilities of the R and T groups are expected to be high, with a coefficient of variation (CV) greater than 0.3. Hence, the FDA recommended, reference-scaled ABE (RSABE) bioequivalence approach for highly variable drugs is proposed.

As there is no FDA guidance for using RSABE in a parallel groups design, the current guidance for cross-over trials (see [\[Draft Guidance on Bioequivalence, 2001\]](#), [\[Draft Guidance on Progesterone, 2011\]](#)), has been modified for application in a parallel groups design.

The between-subject variability for the R group will take the place of the within-subject variability for R.

A mixed scaling approach will be used: (1) if the standard deviation of the R group data (on the log scale) exceeds 0.294, the traditional ABE limits of $\ln(0.8)$ and $\ln(1.25)$ will be scaled by the between-subject variability for the R group, (2) otherwise the standard TOST (two one-sided tests) approach for (unscaled) ABE will be used. The regulatory constant used in the linearised criterion for the RSABE approach will be set to $\sigma_0 = 0.25$ (as in the recommended RSABE approach for cross-over trials).

The steps in the analysis will therefore be:

1. Calculate s_R the standard deviation of the R group subjects' data on the log-scale (for AUC_{tau} or C_{max}).
2. If $s_R < 0.294$ then apply the standard ABE criteria, i.e., determine if the 90% confidence interval for the mean difference between T and R on the log-scale, $(\mu_T - \mu_R)$, lies within $[-\ln(1.25), \ln(1.25)]$.

3. If $s_R \geq 0.294$ then apply the reference scaled ABE criteria, i.e., determine if, $-\theta_s \leq \frac{(\mu_T - \mu_R)}{s_R} \leq \theta_s$ where $\theta_s = \frac{\ln(1.25)}{\sigma_0}$, and $\sigma_0 = 0.25$. This is done by calculating an approximate 95% upper confidence bound for the linearised criterion, $(\mu_T - \mu_R)^2 - \theta_s^2 \sigma_R^2$. If this upper bound is less than or equal to zero and the point estimate of the T/R geometric mean ratio (GMR) falls within (0.8, 1.25), then ABE is declared (i.e., the null hypothesis is rejected).

Testing will be performed as above for AUCtau and Cmax separately on the BE analysis set.

2.5.3 Handling of missing values/censoring/discontinuations

Missing data will not be imputed in general for any analyses. Only patients with non-missing data will be included in the relevant analyses.

2.5.4 Supportive analyses

No additional analysis is planned for the primary objective.

2.6 Analysis of the key secondary objective

There is no key secondary objective.

2.7 Analysis of secondary objective(s)

2.7.1 Secondary endpoints

Secondary endpoints include:

- PK endpoints (i.e., concentration by time point, AUCtau, and Cmax at week 8 dosing interval)
- Positive ADA by time point

2.7.2 Statistical hypothesis, model, and method of analysis

Analysis of secondary endpoints include:

- Summary statistics of concentration by time point will be provided for each of the four treatment groups on the PK analysis set. Descriptive summary will also be provided for AUCtau and Cmax at week 8 dosing interval.
- Proportion of patients with positive ADA will be provided by time point and overall for each of the four treatment groups on the safety set. The proportion will be based on patients with non-missing ADA results at the evaluation time point. A listing by patient will also be provided.

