18-Sep-2019	Prior to DBL	Align with submission planning and update for corrections and clarity	Amendment 2	Section 2.4.1: Add condition of analysis cut-off date for time at risk definition. Section 2.1.2.1: [REDACTED] [REDACTED] to account for some assessments occurring outside the original definitions Sections 2.1.2.1, 2.8.3.2, 5.3.1: Remove left-over reference to T-cell assessment (T-cell analysis was already removed from previous amendment, due to panel unavailable at the study start) Section 2.3.5: Remove entirely (smoking and alcohol history information not needed in listings) Section 2.5.1: Clarify exclusion of concentrations / patients from BE analysis due to missing concentration value or dose missed due to reasons that are not protocol deviations (missed dose leads to the exclusion of two patients at the time of amendment). [REDACTED] Section 2.8.6: Final naming decision for Registration and Final CSR.

Date	Time point	Reason for update	Outcome for update	Section and title impacted (Current)
21- Oct- 2019	After DBL	Correct inaccurate reference to PD ID INCL01 and 	Addendum 1	
Section 4:  
 
Other minor corrections or clarifications made in the document.
 
Section 2.8.3.4: Other special lab results
 
Updates are made in order to provide more accurate information on 
  
2) correct the data cutoff for 
  
Same section: correction of error in explanation of notably low IgM/IgG criteria.
 
Section 5.6: Rule of exclusion criteria of analysis sets

Date	Time point	Reason for update	Outcome for update	Section and title impacted (Current)

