2.2 Analysis sets

All screened patients (SCR): The SCR set comprises all patients who were screened.

BE analysis set: All patients randomized to PFS (Abdomen) or AI (Abdomen) treatment arms with PK data during dosing interval starting at Week 8. Patients will be grouped by the randomized treatment. Major deviation from the randomized treatment as defined in [Table 5-5](#) and [5.6](#) will result in exclusion of patients from the primary analysis.

PK analysis set: All patients randomized to PFS (Abdomen) or PFS (Thigh) or AI (Abdomen) or AI (Thigh) treatment arms with PK data during dose administrations. Patients will be grouped by the randomized treatment.

Safety set: All patients randomized and have taken at least one dose of study drug. Patients will be grouped by the actual treatment received. If patients received study treatment different from the randomized treatment accidentally during the study, they will be analyzed according to the treatment to which they were exposed longer in duration.

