5.6 Rule of exclusion criteria of analysis sets

Patient classification in the analysis sets is entirely based on protocol deviation and non-protocol deviation criteria. Details are provided in [Table 5-5](#) and [Table 5-6](#).

Table 5-5 Protocol deviations that cause patients to be excluded

Deviation ID	Description of Deviation	Exclusion in Analysis sets
	Informed consent obtained = 'No' or missing[#]	Excluded from all analysis sets
TRT04	Administration of study drug to wrong site of body at week 8	Excluded from BE analysis set
TRT05	Administration of study drug using incorrect device at week 8	Excluded from BE analysis set
TRT06	Patient missed injection at any visit in the treatment phase	Excluded from BE analysis set

[#] No deviation ID was assigned in the database to this event

Table 5-6 Patient Classification

Analysis Set	PD ID that cause patients to be excluded	Non-PD criteria that cause patients to be excluded
SCR	NA	NA

Analysis Set	PD ID that cause patients to be excluded	Non-PD criteria that cause patients to be excluded
BE	Informed consent obtained = 'No' or missing, TRT04; TRT05, TRT06	Not assigned a valid randomization number
PK	Informed consent obtained = 'No' or missing	Not assigned a valid randomization number
SAF	Informed consent obtained = 'No' or missing	No study drug taken

6 Reference

Cockcroft DW, Gault MJ (1976) Prediction of creatinine clearance from serum creatinine. *Nephron*; 16:31-41

FDA Draft Guidance on Progesterone (2011)

https://www.accessdata.fda.gov/drugsatfda_docs/psg/Progesterone_caps_19781_RC02-11.pdf

FDA Guidance for Industry (2001) Statistical Approaches to Establishing Bioequivalence. <https://www.fda.gov/regulatory-information/search-fda-guidance-documents/statistical-approaches-establishing-bioequivalence>

Garwood F. (1936) Fiducial Limits for the Poisson Distribution. *Biometrika* 28, 437-442.

Nilsson M. et al. (2013) Columbia-Suicide Severity Rating Scale. Scoring and data analysis guide.

Novartis: Philippe Close (2011): *Hepatotoxicity: Clinical Development Safety Guideline*.

Sahai H, Khurshid A (1993). Confidence intervals for the ratio of two Poisson means. *The Mathematical Scientist*, 18, 43–50.

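### The Week 8 AUCtau/Cmax summaries by injection site apply no wrong-site, wrong-device or missed-dose exclusion, so thigh patients with these deviations stay in their randomized arm (minor; descriptive secondary objective only)

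*SAP*

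**What the plan says.** The secondary PK objective is to characterise AUCtau and Cmax after injection in the abdomen or the thigh (Protocol Table 2-1). Protocol 6.7.2 compares group 3 with group 1 and group 4 with group 2, that is, thigh with abdomen within each device.

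- **Analysis set.** Protocol 9.5 puts the AUCtau/Cmax summaries for the four groups on the PK analysis set. SAP 2.7.2 names that set for concentrations and then adds: "Descriptive summary will also be provided for AUCtau and Cmax at week 8 dosing interval". It names no other set and no exclusion, and SAP 2.7.3 marks the handling of missing values as not applicable.
- **Who is in the PK set.** SAP 2.2: "All patients randomized to PFS (Abdomen) or PFS (Thigh) or AI (Abdomen) or AI (Thigh) treatment arms with PK data during dose administrations". Patients are grouped as randomized. The major-deviation exclusion in the same section is tied to the primary analysis.
- **Deviation rules.** SAP Table 5-5 lists "Administration of study drug to wrong site of body at week 8" (TRT04), "Administration of study drug using incorrect device at week 8" (TRT05) and "Patient missed injection at any visit in the treatment phase" (TRT06). Each has one consequence: removal from the BE set.
- **PK set exclusions.** In SAP Table 5-6 these are missing consent and "Not assigned a valid randomization number". No TRT code appears.
- **Missed doses.** SAP 2.5.1 says "concentrations will be flagged and indicated in the data listing for exclusion from the BE analysis in case one or more doses were missed", counting doses up to and including Week 8. The patient's PK parameters are then dropped from the BE analysis.
- **Recorded cases.** The SAP document history for Amendment 2 notes: "missed dose leads to the exclusion of two patients at the time of amendment".

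**The concern.** The sponsor treats these deviations as serious enough to invalidate a patient's Week 8 parameters when devices are compared. Thigh patients are never in the BE set, so none of the rules can reach them. The gap matters most for TRT04: injection site is the factor being characterised, yet a wrong-site injection has no consequence in the summary that characterises it.

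Two distortions follow. A wrong-site patient keeps the randomized label and pulls the two site summaries together. A patient who missed a dose can contribute lower exposure for a reason unrelated to site. One patient is 1/12 = 8.3% of a thigh arm. The abdomen arms can also show two different AUCtau/Cmax summaries, one on the BE set and one on the PK set, with no stated reason for the difference.

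**Working it through.** **1. The plan's own precision figure.** Inputs from SAP 3.2: CV 85%, n = 60 against 12, 90% CI width 0.78.

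- σ = √ln(1 + 0.85²) = 0.7374
- Width = 2 × t(0.95, 70 df) × σ × √(1/60 + 1/12) = 0.777

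This reproduces 0.78 on the log scale.

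**2. Wrong site at Week 8.** Let m of 12 thigh patients show abdomen-type exposure but be counted as thigh. The log site difference is multiplied by 1 − m/12:

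- m = 1: 0.917
- m = 2: 0.833

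For an assumed true thigh/abdomen ratio of 0.80, the observed ratio becomes 0.80^0.917 = 0.815 (m = 1) or 0.80^0.833 = 0.830 (m = 2).

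This treats the whole Week 8 to 12 exposure as abdominal. If only the Week 8 injection was misplaced, carry-over from earlier thigh doses softens the effect. With the shares from step 3, the patient's exposure relative to abdomen is 0.514 × 1 + 0.486 × 0.80 = 0.903. The arm's mean log ratio is then (11 × ln 0.80 + ln 0.903)/12 = −0.213, a ratio of 0.808. So 92% is the larger effect for one patient.

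**3. Missed dose.** Assumptions: linear, mono-exponential, bolus-like kinetics, with sampling continued over Week 8 to 12. The half-life of 20 days is taken from the SAP's safety cut-off of 5 × 20 days. A dose given d days before Day 56 has weight 2^(−d/20).

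| Dose | Weight at Day 56 | AUC ratio if missed | Factor on a 12-patient geometric mean |
|---|---|---|---|
| Day 7 | 0.183 | 1 − 0.183/1.944 = 0.906 | 0.906^(1/12) = 0.992 |
| Day 14 | 0.233 | 0.880 | 0.989 |
| Week 4 | 0.379 | 0.805 | 0.982 |
| Week 8 | 1.000 | 0.944/1.944 = 0.486 | 0.942 |

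The Day 1 weight is 0.149 and the weights sum to 1.944. A missed Day 7 dose lowers the geometric mean by about 0.8%, a missed Week 4 dose by about 1.8%, and a missed Week 8 dose by about 5.8%.

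The Week 8 figure depends on the half-life. The factor is 0.954 at 26 days, 0.915 at 14 days and 0.875 at 10 days.

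**4. The two recorded patients.** They were excluded from the BE analysis, which contains only abdomen arms of about 60. If Week 8 was the missed dose and a value was derived, each shifts an arm's geometric mean by 0.486^(1/60) = 0.988, about 1.2%. If both are in one arm the factor is 0.976. At a 14-day half-life the single-patient factor is 0.346^(1/60) = 0.982.

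**The case against.** The strongest reply is about size and likelihood.

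- The site summary is descriptive. Both documents say it does not aim to show bioequivalence and that no formal test is planned.
- A 90% CI width of 0.78 is a factor of about exp(0.39) = 1.48 either way, so shifts of 1% to 6% are small beside it.
- Both documents expect no clinically significant difference between sites. If that is right, mislabelling one patient changes almost nothing.
- Injections are given at the site by a health care provider or study nurse (Protocol 5.5.4). Packs are linked to the arm, injection location and visit (Protocol 5.3 and 5.5.2).
- Deviations are summarised by category and all data are listed, so affected patients could be traced.
- Keeping every randomized patient with PK data is a defensible choice for a descriptive table.

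All of this limits the consequence. It does not supply the missing rule: a listing leaves the table unchanged, and an expectation of no difference is what the thigh arms are there to examine. The discretion in SAP 2.5.1 to flag missing or below-LOQ values does not cover wrong site, wrong device or missed doses.

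A reader might infer two stronger claims that the documents do not support. The first is that patients who missed Week 8 are certainly in the AUCtau/Cmax table. SAP 2.5.1 defines both parameters from data after the Week 8 dose, so a value may never be derived. The second is that the two recorded missed-dose patients show contamination of the thigh arms. They are abdomen patients, and the documents state neither which dose they missed nor whether they have Week 8 to 12 values in the PK-set summary.

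**Conclusion.** The gap in the rules is real. No written site, device or missed-dose exclusion applies to the four-arm Week 8 AUCtau/Cmax summaries, and none can reach a thigh patient. The wrong-site and wrong-device cases are the clearest, because those patients have usable Week 8 profiles under the wrong label.

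The size is modest. One misplaced patient of 12 shrinks the log site difference to about 92% of its true value at most. One missed dose before Week 8 moves a thigh geometric mean by about 1% to 2%. The 6% figure is an illustration that needs a missed Week 8 dose, a derived value and a half-life near 20 days. The two recorded patients would move an abdomen arm by about 1.2% each under those same conditions. No thigh case is recorded.

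Only a descriptive secondary objective is affected. The primary BE test keeps its exclusions and is untouched. Severity is minor.

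**What to change.** In SAP 2.7.2 and Table 5-6, apply three exclusions to the Week 8 AUCtau and Cmax summaries in all four arms: TRT04, TRT05, and any dose missed up to and including Week 8. Keep the full PK set for the concentration listings, with affected patients flagged.

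Use the SAP 2.5.1 limit for missed doses rather than the wording of TRT06. TRT06 covers the whole treatment phase, and PK sampling is before dosing (Protocol 6.2), so a missed Week 12 injection falls after the interval being summarised. The two rules should be reconciled.

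The cost is a sentence of text, an entry in Table 5-6 and one filter in the table program. Precision falls slightly: by the formula in step 1, the 90% CI width goes from 0.777 to 0.807 with one thigh patient removed (60 against 11) and to 0.840 with two (60 against 10). Removing two abdomen patients instead gives 0.780 (58 against 12).

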2.7.3 Handling of missing values/censoring/discontinuations

Not applicable.

2.8 Safety analyses

Safety analyses will be conducted using the safety (SAF) set. Patients will be grouped by the actual treatment received. If patients received study treatment different from the randomized treatment accidentally during the study, they will be analyzed according to the treatment to which they were exposed longer in duration. Unless explicitly stated otherwise, only data up to and including the safety cut-off of 100 days after last administration of study drug will be included in the analysis and data beyond this time point for a given patient will be excluded from the safety analysis. The safety cut-off of 100 days (5 x 20 days) takes the long half-life of the investigational drug into account.

The assessment of safety will be primarily based on the frequency of adverse events (including death and non-fatal serious adverse events). Additional safety assessments include laboratory tests, physical examination (including examination of skin), vital sign measures, ECG evaluations and assessment of suicidality. Clinically significant findings in these additional safety assessments will be reported as adverse events and analyzed as such. In addition all safety assessments will be summarized or listed as appropriate.

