5.2 Treatment arms

Subjects will be assigned at visit Day 1 to one of the following 4 treatment arms in a ratio of 5:5:1:1

- PFS (abdomen): ofatumumab 20 mg sc. injection with PFS administrated on abdomen
- AI (abdomen): ofatumumab 20 mg sc. injection with AI administrated on abdomen
- PFS (thigh): ofatumumab 20 mg sc. injection with PFS administrated on thigh
- AI (thigh): ofatumumab 20 mg sc. injection with AI administrated on thigh

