2.1.1 General definitions

Below summarize some general definitions to be used in the rest of the document.

Table 2-2 General definitions

Study treatment/Study drug	The investigational drug ofatumumab injected by PFS or AI devices will be referred as study treatment or study drug.
Date of first administration of study drug/first dose date	The first injection date of ofatumumab.
Date of last administration of study drug/last dose date	The last injection date of ofatumumab.
Study Day 1 or Day 1	The date of first administration of study drug/first dose date.

Study Day	
All other study days will be labeled relative to Day 1. For events with dates on or after Day 1, study day for the event is calculated as (event start date – first dose date + 1). For events with dates before Day 1, study day for the event is calculated as (event start date – first dose date).
 
Day 0 will not be used.

Duration of an event	Duration of an event is calculated as (event end date – event start date +1).
1 month	30 days; to be used in defining 3-month or 6-month confirmed disability worsening or improvement.
4 weeks	28 days; to be used in determining target days of scheduled visits. It is based on the scheduled injection frequency for ofatumumab (during the maintenance phase).
Day post-study drug discontinuation	Day post-study drug discontinuation for a particular event is calculated as (event start date – study drug discontinuation date).
Baseline	
Baseline is the last assessment obtained prior to the first administration of study drug. No visit windows will be needed for the identification of baseline assessment.
 
For pulse and blood pressure vital sign values, the baseline is the average of the non-missing values of the 3 measurements taken on the last visit prior to the first administration of study drug. The pre-injection assessment values on Day 1 vital sign CRF page will not be used for baseline derivations.

On-treatment period	On-treatment period includes days from the first injection date until 30 days after the last injection date; This definition considers patients are scheduled to inject every 28 +/- 3 days. The on-treatment definition applies to efficacy analyses only.

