2.8.1.1.1 Injection reaction related AEs

Incidence of injection site reaction AEs and injection systemic reaction AEs as collected in the relevant CRF pages will be reported as part of the AE summary tables as two preferred terms respectively.

Additionally, incidence of injection site reaction AEs and injection systemic reaction AEs will be reported separately for each injection.

For summaries of injection systemic reaction AEs specified in this section, reaction/symptom start date and time will be compared with the injection date and time. Only reactions/symptoms within 24 hours after injections will be included (i.e., time to onset of reaction \leq 24 hours). The time to onset of reaction will be derived as (reaction start date/time – injection date/time).

Symptoms listed in the injection site reaction or injection systemic reaction CRF pages will be summarized by providing the number and percentage of patients with each of the symptoms and pre-specified grouping of symptoms as well as overall. These summaries will be provided for each injection as well as cumulatively for all injections.

For the injection site reaction, no grouping of symptoms will be specified. For the injection systemic reaction, symptoms will be grouped under 6 categories as defined below and the number and percentage of patients with at least one symptom reported under the category will be provided for each category.

- Skin/mucosal tissue symptoms: Rash, Urticaria, Pruritus general, Flushing
- Respiratory compromise: Dyspnea, Bronchospasm, Chest discomfort, Cough
- Related to change in vital signs: Hypotension, Hypertension, Dizziness, Tachycardia
- Gastrointestinal symptoms: Nausea, Vomiting, Abdominal pain, Diarrhea
- Musculoskeletal/connective tissue symptoms: Arthralgia, Myalgia, Back pain
- Other manifestations: Fever, Headache, Chills, Asthenia, Fatigue, and Other

For the injection systemic reaction, time to onset of the first symptoms after each injection will be summarized by cumulative hour intervals (i.e., 0 to 1, 0 to 2, 0 to 3, etc. until 0 to 24 hours). These summaries will be provided for each injection as well as cumulatively for all injections.

The proportion of patients with injection site reactions and the proportion of patients with injection systemic reactions will be plotted by treatment group against the injection sequence numbers (injections 1, 2, 3, 4, 5, 6 etc.).

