For the first 3 injections, additional summaries will be provided by category of injection related premedication. Specifically, 9 categories are defined as 1) no injection related premedication, 2) type 1, 3) type 2, 4) type 3, 5) type 1+ type 2, 6) type 1+ type 3, 7) type 2+ type 3, 8) type 1+ type 2+ type 3, 9) Any injection related premedication. The types 1 to 3 refer to protocol specified three types of injection related premedication as stated in [Section 2.4.2.3](#).

A separate listing for injection site reaction AEs and injection systemic reaction AEs will be provided where all reported injection related reactions (IRR) (regardless of timing) will be listed along with the corresponding injection sequence number and time to onset from the most recent injection as well as from Day 1. The listing will be sorted by injection of first occurrence of symptoms. Specifically, under the first injection, patients whose first IRR was associated with the first injection will be listed; within a patient all IRRs to all injections will be listed chronologically. Under the second injection, patients whose first IRR was associated with the second injection will be listed; similarly, within a patient all IRRs to all injections will be listed chronologically. The listing will continue with subsequent injections until all patients with IRRs are included in the listing.

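### Reaction outputs reported injection by injection inherit a patient-level longest-exposure grouping, so a reaction to a single wrong-device or wrong-site injection would appear under the device or site not used (low priority)

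*SAP*

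**What the plan says.** - **Grouping rule.** SAP 2.2 defines the set: "Safety set: All patients randomized and have taken at least one dose of study drug. Patients will be grouped by the actual treatment received". For accidental mixed exposure, SAP 2.2 and 2.8 both say that "they will be analyzed according to the treatment to which they were exposed longer in duration". In 2.8 this governs the safety analyses as a whole.
- **What a treatment is.** The four arms in Protocol 5.2 combine device and body site, for example "PFS (thigh): ofatumumab 20 mg sc. injection with PFS administrated on thigh". SAP Table 2-2 is narrower: "The investigational drug ofatumumab injected by PFS or AI devices will be referred as study treatment or study drug". It does not mention body site.
- **Injection-level outputs.** SAP 2.8.1.1.1 says that "incidence of injection site reaction AEs and injection systemic reaction AEs will be reported separately for each injection". It asks for symptom summaries per injection as well as cumulatively. It also asks for a figure in which the proportions of patients with reactions "will be plotted by treatment group against the injection sequence numbers".
- **Listing.** Reported reactions "will be listed along with the corresponding injection sequence number and time to onset from the most recent injection". Device and body site used are not among the items named.
- **Errors provided for.** SAP Table 5-5 has a deviation code for "Administration of study drug to wrong site of body at week 8" (TRT04) and a matching one for the wrong device at Week 8 (TRT05). Both exclude a patient from the BE set only.

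**The concern.** Assigning a patient to the treatment with the longer exposure is sensible for events that cannot be tied to one dose. An injection reaction is different: it belongs to a particular injection, given with a particular device in a particular body area. The plan presents these reactions at that level, but groups them with a rule that works on the whole patient.

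The rule comes into play only when a patient has received something other than the randomized treatment. For the per-injection outputs, that is the case in which it gives the wrong attribution. Injection-related reactions are named within the safety endpoint (SAP Table 1-1). They are also the safety outcome most closely linked to device and site, in a study meant to bridge from the syringe to the autoinjector. At stake is the accuracy of a few descriptive proportions, mainly in the two small thigh arms.

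**Working it through.** The plan states no figure to reproduce on this point. The check has three steps.

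**1. Can one wrong injection move the patient to another column?**
Inputs: injections on Days 1, 7, 14, 28, 56 and 84, and exposure = last − first + 31 days (both SAP 2.4.1). The SAP does not say how to split exposure between treatments. I assume that each injection covers the days until the next one and that the last covers 31 days.

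| Injection | 1 | 2 | 3 | 4 | 5 | 6 | Total |
|---|---|---|---|---|---|---|---|
| Days covered | 6 | 7 | 14 | 28 | 28 | 31 | 114 |

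The total agrees with the SAP formula: 84 − 1 + 31 = 114. One injection covers between 6/114 = 5.3% and 31/114 = 27.2% of exposure, always under half. In a patient who follows the full schedule, a single wrong injection therefore never changes the column, and a reaction to it stays under the device or site not used.

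Longer runs of error behave in the same way:
- First three injections different: 6 + 7 + 14 = 27 days against 87. All three are shown under the later treatment.
- First four different: 27 + 28 = 55 days against 28 + 31 = 59. Four of the six injections are shown under the treatment used for only two.

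**2. Does the wording of the rule matter?**
The phrase about treatment group is explicit in 2.8.1.1.1 only for the figure. For the tables, the grouping follows from 2.8. If treatment means device and site, the longer-exposure rule applies to both kinds of error, with the result above. If it means device only (Table 2-2), a wrong-site injection does not trigger the rule. The patient then stays in the assigned site column, and the reaction is again shown under the site not used.

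**3. How large is the effect on one per-injection proportion?**
Inputs: 62 patients per abdomen arm and 13 per thigh arm (SAP 1.1). Let a column of n patients show x reactors, one of them misplaced. With correct classification that patient leaves both numerator and denominator, so the change is

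x/n − (x − 1)/(n − 1) = (n − x) / [n(n − 1)].

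- Thigh arm, n = 13: (13 − x)/156. With x = 1 this is 12/156 = 7.7 points; with x = 6, 7/156 = 4.5 points; with x = 13, zero.
- Abdomen arm, n = 62: (62 − x)/3782. With x = 1 this is 61/3782 = 1.6 points, and it falls as x rises.

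The maxima equal 1/13 and 1/62. A wrong injection without a reaction also matters slightly, because it leaves a non-reactor in the wrong denominator: x/12 − x/13 = x/156 in a thigh arm, or 3.8 points with x = 6, in the opposite direction.

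**The case against.** **The event may never happen.** The effect needs a wrong-device or wrong-site injection. Site staff give every injection (Protocol 5.5.4), and IRT issues medication numbers that correspond to an arm and a visit (Protocol 5.3 and 5.5.2). No error rate is given. A reader might infer from TRT04 and TRT05 that such errors were expected or had occurred. The codes show only that the sponsor provided for them at Week 8, for the BE set. This objection stands and limits the priority.

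**The rule is conventional and the output descriptive.** This also stands. Longest exposure is an ordinary choice for general adverse event tables, and no test of reactions between devices or sites is planned.

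**Affected cases could be traced.** Treatment errors are recorded in the CRF (Protocol 7.5), deviations are summarized (SAP 2.3.1), and all data are to be listed (SAP 2.1). This holds in part. The reaction listing as specified names neither device nor site, so the misplacement would not be visible there.

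**Attenuation.** A reader might infer that misplacement always pulls the device or site profiles together. That could hold on average, but one misplaced reaction can also widen an observed difference. The documents do not support a definite direction.

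**Any change breaks reconciliation.** Per-injection and cumulative tables would group an affected patient differently, and lines in the figure would no longer follow a fixed set of patients. This is a real cost, which a footnote can handle.

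**Conclusion.** The point holds as a narrow gap. The patient-level rule in SAP 2.8 is not overridden for the injection-level outputs in 2.8.1.1.1. In a patient on the full schedule, it shows a reaction to a single wrong-device or wrong-site injection under the device or site not used.

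The size is zero if no such injection occurs. Otherwise each misplaced reactor changes the proportion in the column that wrongly holds it by at most about 7.7 points (thigh) or 1.6 points (abdomen). These are ceilings, reached when that column has no other reactor at that injection; they are not the effect of every misplaced reaction.

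The figures assume the planned arm sizes and the exposure split above. In a patient who stops early, one wrong injection could be the longer exposure, and the rule would then misplace the correctly given injections instead.

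A stronger conclusion, that the safety comparison or the bioequivalence result is compromised, is not supported. Bioequivalence rests on AUCtau and Cmax in the BE set, which has its own exclusion rules for wrong device and wrong site at Week 8.

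**What to change.** In SAP 2.8.1.1.1:
- Classify each injection in the per-injection incidence tables, the per-injection symptom tables and the figure by the device and body site actually used at that injection. The denominator is the patients who received that injection in that way.
- Add device and body site used to the injection reaction listing.
- Keep the longer-exposure rule for the overall adverse event tables and the cumulative reaction summaries. Add a footnote identifying affected patients, because their per-injection and cumulative columns will not fully reconcile.

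The cost is about one sentence in the SAP, a small programming change and the footnote. It presupposes that device and site are recorded for each injection. The longer-exposure rule already needs treatment by injection, and treatment errors go in the CRF. However, Protocol 6.4 lists only dosages and visit intervals, and the CRF is not among the documents, so this should be confirmed. Cumulative summaries would still carry the misattribution for affected patients, which the footnote discloses. If no error occurred, no result changes.
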